1. INTRODUCTION AND BACKGROUND

Fungal corneal ulcers, because of their poor outcomes and the lack of evidence to guide treatment, present a therapeutic challenge to clinicians.¹ The incidence of fungal keratitis varies by region, which is thought to be due to differences in climate as well as risk of corneal trauma.^{1,2} In the tropics, fungal infection can account for upwards of 50% of corneal ulcers.^{1,3,4} In the United States fungal keratitis ranges from 35% of corneal ulcers in South Florida⁵ to 4% in temperate climates such as Los Angeles.⁶ The Mycotic Ulcer Treatment Trial I (MUTT I), a NEI-funded randomized double masked clinical trial found that natamycin is superior to voriconazole for the treatment of filamentous fungal ulcers and in particular for *Fusarium* species.⁷ However, natamycin is fungistatic and has limited penetration into the corneal layers.⁸

Voriconazole may still be an important adjunct in the treatment of fungal ulcers. *In vitro* studies suggest that voriconazole should have good efficacy against *Aspergillus* and *Fusarium*.⁹ Intrastromal injection of voriconazole may provide steady state drug concentrations at the site of infection and avoid intervals of sub-therapeutic drug dosing. Secondly, the identity of the organism may play an important role in guiding treatment. Ulcers caused by *Aspergillus* species did equally well with topical voriconazole and natamycin, whereas those caused by *Fusarium* species had 4 lines worse visual acuity at 3 months. Possibly, *Aspergillus* ulcers will fare better when oral voriconazole is added. Thirdly, there may be presenting characteristics, such as deep stromal involvement, which could predict a benefit from intrastromal voriconazole injection.

Studies of intrastromal injection of voriconazole have yielded mixed results. Several case series have found intrastromal voriconazole to be beneficial.¹⁰⁻¹² However, one randomized controlled trial, comparing intrastromal injection to topical voriconazole found significantly improved 3-month visual acuity in the topical voriconazole group.¹³ However, in the intrastromal voriconazole arm there were more central ulcers than in the topical voriconazole arm and scar size between the two groups was comparable implying that intrastromal injection does not lead to worse scarring. In this study we will evaluate the effectiveness of intrastromal voriconazole injection in addition to topical natamycin treatment for the treatment of moderate to severe fungal keratitis.

Research Question: Is intrastromal injection of voriconazole beneficial in addition to topical natamycin in the treatment of filamentous fungal corneal ulcers?

1.1 Specific Aims:

- 1) **Does the addition of intrastromal injection of voriconazole decrease the rate of repeat 3-day culture positivity compared with medical management?** We hypothesize that there will be decreased 3-day repeat culture positivity in the intrastromal voriconazole injection group.
- 2) **Does intrastromal injection of voriconazole improve best spectacle corrected visual acuity at 3 months compared with medical management?** We hypothesize that intrastromal injection with voriconazole will improve 3-month visual acuity compared with topical natamycin alone.
- 3) **Does the addition of intrastromal injection of voriconazole improve 3-month scar size, days to re-epithelialization and rate of perforation/need for Therapeutic penetrating keratoplasty (TPK) compared with medical management?** We hypothesize that there will be improved 3-month scar size and decreased perforation rate in the intrastromal voriconazole group, but no difference in days to re-epithelialization.

1.2 Study Outcomes:

Primary Outcome:

- Microbiological cure on 3-day repeat cultures

Secondary Outcomes:

- BSCVA at 3 months
- Microbiological cure on 7-day repeat cultures
- Scar size/depth, as measured by clinical exam, slit lamp photographs and OCT
- Adverse events including rate of perforation/need for TPK
- Thinning as measured by pachymetry and OCT
- Topography
- Difference in IND-VFQ at 3 months between groups
- Corneal neovascularization, as measured by clinical exam & slit lamp photographs

1.3 Study Design:

Mycotic Antimicrobial Localized Injection (MALIN) is a randomized, masked, two-arm clinical trial. The purpose of the study is to determine differences in microbiological cure for 3-day repeat cultures between different antifungal treatments. There will be 1:1 randomization to one of these two treatment groups: 1) Topical natamycin plus intrastromal voriconazole injection or 2) Topical natamycin alone. The enrollment period will be 3 months.

3. PATIENT FLOW

3.1 Study Timeline

The enrollment period will be 3 months. Study participants will be required to have 4 follow-up visits at 3 days, 7 days, 1 month, and 3 months (visit window: 2.5 -3.5 months). All study participants will be admitted to the hospital for 7 days. Additional visits may be needed and will be determined by the physician/investigator.

3.2 Eligibility Requirements

Only those who meet all of the inclusion criteria and none of the exclusion criteria will be enrolled in this study.

Inclusion criteria:

- Moderate to severe corneal ulcer that is smear positive for filamentous fungus
- Pinhole visual acuity worse than 20/70 in the affected eye
- Age 18 years or greater, and less than or equal to 70 years
- Basic understanding of the study as determined by the physician
- Commitment to return for follow up visits

Exclusion criteria:

- Gram stain positive for bacteria or evidence of other concomitant infection (i.e. herpes, acanthameoba)
- Impending or frank perforation at recruitment
- Involvement of sclera at presentation
- Non-infectious or autoimmune keratitis
- History of corneal transplantation or recent intraocular surgery
- No light perception in the affected eye
- Pinhole visual acuity worse than 20/200 in the unaffected eye
- Pregnant women
- Participants who are decisionally and/or cognitively impaired

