3.4.8 Final Visit. At the 3- Month visit study participants will have their BSCVA and slit lamp examination recorded, in addition to repeat photography, topography and OCT and be administered the IND-VFQ. Endothelial cell count will also be measured. Adverse events will be reviewed and recorded.

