4. PROCEDURES

4.1 Masking

All study participants will be masked to their intervention. The refractionist performing the BSCVA will also be masked. Due to the nature of the intervention, the surgeon and technician performing intrastromal injection will not be masked, however, the physician performing repeat scraping as well as the microbiologist will be masked to treatment arm. UCSF study personnel will not be given any identifying information.

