- We will compare BSCVA between the two groups, at the 3-month time period (between 2.5-3.5 months) using the Wilcoxon rank sum with a 2-sided alpha of 0.05. For study participants who experience perforation or undergo TPK this will be noted and a BSCVA will be performed prior to performing further surgery, this last observation will be carried forward (LOCF) as the 3-month BSCVA. An enhanced analysis using standard longitudinal modeling methods will be used to handle data from study participants who are lost to follow up.
- We will compare 7-day culture positivity between the two groups using a logistic regression model (dichotomous culture positive or culture negative outcome) controlling for baseline culture status
- Scar size as measured on clinical exam and photographs
- Corneal topography
- Corneal Thickness and scar size as measured by OCT
- IND-VFQ will be compared between the two groups controlling for baseline VFQ
- Analyses of perforations or other adverse events
- A cost effectiveness analysis will be performed

6. Interim Monitoring

A masked interim analysis will be conducted to re-evaluate sample size based on 3-day culture positivity when one-third of the data have been collected. A medical monitor will be appointed at UCSF to monitor any serious adverse events. A small DSMC at UCSF will be appointed to conduct an un-masked interim analysis to evaluate for futility or harm.

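### The IND-VFQ comparison relies on a baseline score that the protocol does not schedule and leaves unused the fellow-eye acuity assessed at screening: a modest, cheaply recovered loss of precision

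*Protocol*

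**What the plan says.** Protocol 1.2 lists among its secondary outcomes "Difference in IND-VFQ at 3 months between groups" and names no covariate. SAP section 5 gives the analysis in one line: "IND-VFQ will be compared between the two groups controlling for baseline VFQ". It names no regression model and no other covariate.

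The baseline score is not in the visit plan. Protocol 3.4.1 (Baseline Visit) lists a baseline form, BSCVA, photography and OCT, but no IND-VFQ. Protocol 3.4.8 (Final Visit) includes "repeat photography, topography and OCT and be administered the IND-VFQ". The schedule in Protocol 3.5 has a single mark on the IND-VFQ row, which reads as Month 3.

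On acuity, Protocol 3.2 requires "Pinhole visual acuity worse than 20/70 in the affected eye" for inclusion and lists as an exclusion "Pinhole visual acuity worse than 20/200 in the unaffected eye". Applying the exclusion means assessing the fellow eye's pinhole acuity at screening. Neither document uses that value as a covariate or stratification factor, and neither says that it is kept as a graded value on the baseline form.

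**The concern.** Treatment is assigned to one eye, while the questionnaire is answered by a person who usually sees with two. Every study eye enters worse than 20/70, so in many participants the fellow eye is probably the better one and may account for much of how they report their visual function. The eligible fellow-eye range is wide: 20/20 is log10(20/20) = 0 logMAR and 20/200 is log10(200/20) = 1.0 logMAR. Variation from this source is unrelated to treatment and adds noise to the comparison.

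A baseline IND-VFQ would absorb much of that noise, because the same person with the same fellow eye would answer both times. The SAP evidently counts on this, but the protocol never collects the score. At Month 3 the analyst would therefore have either no baseline adjustment or a covariate chosen after the fact, although a relevant pre-randomisation value had been available at screening. What is at stake is the precision of one secondary outcome.

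**Working it through.** **Inputs.** From the documents: 70 participants (SAP 2) and 1:1 allocation (Protocol 1.3), hence 35 per arm. Two-sided alpha is taken as 0.05 and power as 80%. The documents give no IND-VFQ standard deviation, target difference, power or correlation, so there is no planned figure to reproduce; the SAP's power statement concerns culture status. All correlations below are assumptions, r is taken in absolute value, and results are in units of the Month 3 IND-VFQ SD.

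**Step 1: no adjustment (the position as scheduled).** Detectable difference = (1.960 + 0.842) × √(2/35) = 2.802 × 0.239 = 0.67 SD.

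**Step 2: adjustment for fellow-eye acuity alone.** If its correlation with Month 3 IND-VFQ is r, the residual variance is (1 − r²) of the total. The detectable difference becomes 0.67 × √(1 − r²), and the equivalent unadjusted sample size is 70/(1 − r²). The last column is power for a difference of 0.5 SD, itself an assumption, by the normal approximation.

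| Assumed r | Variance removed | Detectable difference (SD) | Equivalent N | Power for 0.5 SD |
|---|---|---|---|---|
| 0 | 0% | 0.67 | 70 | 55% |
| 0.1 | 1% | 0.67 | 71 | 56% |
| 0.2 | 4% | 0.66 | 73 | 57% |
| 0.3 | 9% | 0.64 | 77 | 59% |
| 0.5 | 25% | 0.58 | 93 | 68% |
| 0.6 | 36% | 0.54 | 109 | 74% |

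**Step 3: cost of the extra parameter.** Estimating one covariate multiplies the variance by about (70 − 3)/(70 − 4) = 67/66 = 1.015. At r = 0.1 this gives 0.99 × 1.015 = 1.005, so there is no gain. At r = 0.2 it gives 0.96 × 1.015 = 0.975, and at r = 0.5 it gives 0.75 × 1.015 = 0.761.

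**Step 4: gain if a baseline IND-VFQ is also in the model.** Let b be the correlation of baseline score with outcome, f that of fellow-eye acuity with outcome, and c that between the two covariates. Then R² = (b² + f² − 2bfc)/(1 − c²), and the further share of remaining variance removed is 1 − (1 − R²)/(1 − b²). The assumed ranges are b = 0.4 to 0.6, f = 0.3 to 0.5 and c = 0.5 to 0.7.

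- Most favourable (b = 0.4, f = 0.5, c = 0.5): R² = (0.16 + 0.25 − 0.20)/0.75 = 0.28, and the further gain is 1 − 0.72/0.84 = 14%.
- Least favourable (b = 0.6, f = 0.3, c = 0.5): R² = (0.36 + 0.09 − 0.18)/0.75 = 0.36 = b², and the further gain is 0%.

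**The case against.** The strongest reply is that the SAP does not plan an unadjusted test. Set against the test it does plan, fellow-eye acuity adds little: 0 to 14% of the remaining variance, and in the most favourable case power for 0.5 SD moves from about 63% to 69%. That stands if a baseline IND-VFQ is obtained. As scheduled it is not, and the table in Step 2 then applies. A reader might take the 9% to 36% reductions as the loss against the SAP's own analysis; they are the loss only while the baseline score goes uncollected.

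It can also be said that the size rests on assumed correlations. That stands. The documents do not describe how IND-VFQ is scored, so dependence on the fellow eye is an inference from its being a questionnaire put to the participant. The 20/200 limit restricts the spread of the covariate, and 20/20 against 20/200 shows the extremes rather than the typical contrast.

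Three stronger inferences are not supported:

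- A reader might infer bias. Randomisation protects the comparison with or without the covariate; only precision is affected.
- A reader might count chance imbalance as a separate harm. The SD of the between-arm difference in mean fellow-eye acuity is √(2/35) = 0.239 SD, so an imbalance of at least 0.3 SD arises in about 21% of randomisations and, at r = 0.5, shifts the contrast by 0.5 × 0.3 = 0.15 SD. That shift is already part of the unadjusted standard error and is the same variance counted above.
- A reader might infer that someone aware of assignment administers the questionnaire, since Protocol 4.4.3 says that the study coordinator knows it. No section says who administers it, and Protocol 4.1 masks the participants, who supply the answers.

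**Conclusion.** The point holds as a matter of precision. The SAP's only IND-VFQ covariate is not scheduled for collection, and a plausible substitute that must be assessed before randomisation goes unused. The benefit of using it is negligible at a correlation of 0.2 or below and material at about 0.5 or above, where the detectable difference falls from 0.67 to 0.58 SD. Which applies cannot be settled from the documents. The figures assume 35 analysable participants per arm. The SAP's assumption of no loss rests on hospital stay to Day 3 and does not extend to Month 3; losses would raise every detectable difference but leave the proportional gain from adjustment nearly unchanged.

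IND-VFQ is one of eight secondary outcomes in Protocol 1.2, and the trial is sized on culture status. This is an optional, inexpensive improvement and does not threaten the trial's main conclusion.

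**What to change.** In SAP section 5, specify linear regression of Month 3 IND-VFQ on treatment arm, with screening fellow-eye pinhole acuity in logMAR as a prespecified covariate. Record that acuity on the baseline form as a graded value, not only as meeting or failing the 20/200 limit.

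In the same edit, reconcile the baseline-score covariate with Protocol 3.4.1 and 3.5. If a baseline IND-VFQ is added to the schedule, keep it in the model alongside fellow-eye acuity. If not, state that fellow-eye acuity replaces it. Make the choice before any unmasked outcome comparison, so that the adjustment cannot appear selected by its result.

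The cost of the acuity covariate is a short SAP amendment, one extra recorded field and one degree of freedom, with no new test or visit. Adding a baseline IND-VFQ would be a further, separate cost: one questionnaire administration per participant.

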3.3 Randomization

Each study eye will be randomly assigned to the 1) Intrastromal voriconazole plus topical natamycin or 2) Natamycin alone. Block randomization will be performed using a computer program (Statistical package R; Version 2.12; R Foundation for Statistical Computing, Vienna, Austria) by the coordinating site.

Once an eye is enrolled in the study, the study coordinator will assign the study participant's eye an ID (alpha-numeric code) and organize the procedure in the operating room within 24 hours. Once the study participant has been assigned a study participant ID and randomized to treatment group, they will be included in the intention to treat analysis.

3.4 Study visits

3.4.1 Baseline Visit. During this visit, eligible patients at Pondicherry will be enrolled in the study and will give consent. The baseline patient form will be completed and BSCVA obtained. All study participants will begin topical therapy with hourly 5% natamycin immediately. They will have baseline photography and OCT. They will then be randomized to either intrastromal voriconazole plus natamycin or topical natamycin alone. Those randomized to intrastromal injection will undergo this procedure in the operating theatre within 24 hours. They will have an additional 2 stromal injections: one on the 3rd day and one on the 5th day. All patients will be admitted to the inpatient setting until the 7th day.

3.4.2 Procedure visit. Within 24 hours of the baseline visit study participants randomized to intrastromal voriconazole will undergo injection in the operating theatre. They will have 2 additional rounds of intrastromal voriconazole injections: one on the 3rd day and one on the 5th day of the study.

3.4.3 Day 3 visit. During this visit, study participants will have slit lamp examination and undergo repeat scraping and culture of the corneal ulcer. Adverse events will also be assessed and recorded. Thereafter, all additional treatments including but not limited to topical voriconazole, or oral ketoconazole, will be at the clinician's discretion. The treating physician will remain masked to treatment arm. After the scraping and culture have been performed, participants randomized to receive intrastromal voriconazole injections will receive an additional injection of voriconazole in the operating theatre.

3.4.5 Day 5 visit. On day 5 participants randomized to receive intrastromal voriconazole injections will receive their final injection of voriconazole in the operating theatre.

3.4.6 Week 1 visit. Approximately one week from enrollment patients will undergo repeat scraping and culture. No other study visit information will be gathered during this visit, therefore any further examination, testing, or treatment will be at the discretion of the treating physician. After the Day 7th day, patients may be discharged from the inpatient setting.

3.4.7 One Month visit. During this visit, study participants will have their BSCVA, slit lamp examination, and OCT performed during this visit. Photography will also be performed. Adverse events will be reviewed and recorded.

3.4.8 Final Visit. At the 3- Month visit study participants will have their BSCVA and slit lamp examination recorded, in addition to repeat photography, topography and OCT and be administered the IND-VFQ. Endothelial cell count will also be measured. Adverse events will be reviewed and recorded.

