3.6 Adverse Events (AEs)

During each study visit, the subject will be questioned about AEs in a non-leading manner. All AEs, whether observed by the Investigator, elicited by the Investigator, or spontaneously reported by the subject, will be documented in the subject's chart and the adverse event form. Slit lamp photography will also be completed after any adverse event takes place.

All AEs should be followed until they are resolved or until a stable clinical endpoint is reached. Each AE is to be classified by the Investigator as SERIOUS (SAE) or NONSERIOUS (NSAE).

If a SAE occurs, the investigator at Aravind Eye Hospital, Pondicherry must fill out the serious adverse event form and email it to [name] at UCSF within 24 hours of the occurrence of the SAE. The investigator must provide written follow-up reports until the SAE or clinically significant AE has resolved or until a stable clinical endpoint is reached. Notification of an SAE or clinically significant AE must also be submitted to the Institutional Review Board (IRB)/Ethics Committee (EC) in accordance with its requirements. All AEs must be reported from the time that the subject provides informed consent through the last study visit.

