4.3 Medical management protocol

In the first 3 days all patients will receive hourly 5% Natamycin, 0.5% Moxifloxacin for prophylaxis every two hours while awake, and 2% homatropine TID. They will be randomized to intrastromal injection with voriconazole versus sham injection. This study requires 7 visits over 3 months including baseline visit, procedure visit, 3-day follow-up and procedure visit, 5-day procedure visit, 1-week follow-up, 1-month and 3-month follow-up. After the 3-day repeat culture visit additional treatments may be added per clinician preference including but not limited to topical voriconazole and oral Ketoconazole.

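### The protocol does not give both arms the same first-week adverse-event questioning: procedure and Day 5 visits are written for the injection arm only, so the AE comparison is at risk of differential ascertainment

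*Protocol*

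**What the plan says.** Protocol section 3.6 ties active questioning to visits: "During each study visit, the subject will be questioned about AEs in a non-leading manner". It also provides for other routes of capture: "All AEs, whether observed by the Investigator, elicited by the Investigator, or spontaneously reported by the subject, will be documented".

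Section 3.4.2 describes the procedure visit for one arm: "Within 24 hours of the baseline visit study participants randomized to intrastromal voriconazole will undergo injection in the operating theatre". Section 3.4.5 does the same for Day 5: "On day 5 participants randomized to receive intrastromal voriconazole injections will receive their final injection of voriconazole in the operating theatre". Neither assigns anything to controls, and section 4.4.3 confines the later injections to the voriconazole arm. Section 3.1 agrees with this reading: "Study participants will be required to have 4 follow-up visits at 3 days, 7 days, 1 month, and 3 months". The procedure and Day 5 visits are not on that list.

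Other text points the other way. Section 4.3 names a sham injection as comparator and says "This study requires 7 visits over 3 months including baseline visit, procedure visit", going on to include the Day 5 procedure visit without separating the arms. Section 6.2 also gives each study eye seven visits. The section 3.5 schedule is a single table for both arms; at Visits 2 and 4 it marks a Procedure form but no Follow-up form.

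The visit descriptions in section 3.4 name AE assessment only at Day 3, Month 1 and Month 3. Section 3.4.6 limits Week 1 study data to scraping and culture, although the schedule marks a Follow-up form there.

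On use of the data, SAP section 5 lists "Analyses of perforations or other adverse events" and SAP section 6 states: "A small DSMC at UCSF will be appointed to conduct an un-masked interim analysis to evaluate for futility or harm".

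**The concern.** If AEs are sought at visits, and one arm has more visits during the treatment week, that arm has more opportunities for an event to be recorded even when true rates are equal. Section 5.3 lists the same local effects (irritation, swelling, pain, redness, discharge) for natamycin and voriconazole. These are the mild, short-lived events whose recording depends on someone asking.

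Any excess would count against injection. AEs are a named secondary outcome and feed an unmasked harm review. With 70 participants randomized 1:1, about 35 per arm, a few extra recorded events could alter how the comparison looks. Contacts that did not take place cannot be recreated after enrollment.

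**Working it through.** The plan gives no figure for AE ascertainment, so there is none to reproduce. The check is a count of contacts by arm, followed by a sensitivity calculation.

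**Step 1. First-week AE contacts under each reading**

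| Reading | Injection | Control | Ratio |
|---|---|---|---|
| (a) 3.6 applied to post-baseline Visits 2–5, with 3.4.2, 3.4.5 and 3.1 taken as written | 4 (V2, V3, V4, V5) | 2 (V3, V5) | 4/2 = 2.0 |
| (b) As (a), baseline also counted | 5 | 3 | 5/3 = 1.67 |
| (c) As (a), Week 1 dropped because of 3.4.6 | 3 | 1 | 3/1 = 3.0 |
| (d) Only visits whose own text names AE assessment (Day 3) | 1 | 1 | 1.0 |
| (e) All participants have seven visits (4.3, 6.2) | 4 | 4 | 4/4 = 1.0 |

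Over the whole trial, post-baseline, reading (a) gives 6 (Visits 2–7) against 4 (Visits 3, 5, 6, 7), a ratio of 1.5. No text says whether controls are questioned on the procedure day or on Day 5, so the documents do not settle which reading applies.

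**Step 2. What unequal contacts could do to recorded AEs**

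Assume equal true risk in both arms. Let *p* be the chance that one questioning contact picks up an event, *s* the chance that it is captured anyway by ward observation or spontaneous report, and *k* the number of contacts. Then

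detection = 1 − (1 − s)(1 − p)^k.

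The documents give neither *p* nor *s*; both are assumed over a range. For reading (a), *k* = 4 and 2. Worked example with s = 0 and p = 0.1: injection 1 − 0.9⁴ = 0.344; control 1 − 0.9² = 0.190; ratio 0.344/0.190 = 1.81.

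| s | p = 0.1 | p = 0.3 | p = 0.5 | p = 0.9 |
|---|---|---|---|---|
| 0 | 1.81 | 1.49 | 1.25 | 1.01 |
| 0.5 | 1.13 | 1.17 | 1.11 | 1.00 |
| 0.8 | 1.04 | 1.06 | 1.04 | 1.00 |
| 0.95 | 1.01 | 1.01 | 1.01 | 1.00 |

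These values belong to reading (a). Under (c) the same extreme corner (s = 0, p = 0.1) would give (1 − 0.9³)/(1 − 0.9) = 0.271/0.100 = 2.71. Under (d) and (e) the ratio is 1.0 throughout.

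**Step 3. Effect of equal contacts**

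If both arms are questioned at the procedure time point and on Day 5, *k* is the same in both arms and the ratio is 1.0 for any *p* and *s*.

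**The case against.** The strongest reply is that the asymmetry may not exist. A sham injection (4.3) would put controls through the same procedure visits, section 6.2 gives everyone seven visits, and section 3.3 has a theatre procedure arranged for each enrolled eye without limiting it by arm. The visit descriptions name AE assessment only at visits that both arms share. This stands: unequal contact is one reading of contradictory text, not an established design feature.

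Second, both arms are inpatients to Day 7, and observed and spontaneous events must be documented from consent onward. This also stands and is why the excess shrinks to 1.06 or less at 80% background capture. It does not close the matter. No AE assessment on the ward is scheduled outside study visits, and on the visit text the injected eyes are additionally seen under the operating microscope by staff whom section 4.1 describes as unmasked. The documents do not say that those staff question participants about AEs, so no more should be made of it than that.

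A reader might infer a doubling of recorded AEs from the 4-to-2 count: if each contact captured only the preceding 24 hours, coverage would be 4/7 = 57% against 2/7 = 29%, a ratio of 2.0. The documents do not support this. They set no 24-hour recall window, and the figure needs zero observed or spontaneous capture in hospitalized patients, contrary to section 3.6. If questioning covers the time since the last contact, both arms are covered for the whole week.

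Third, perforation and TPK, the AEs singled out in section 1.2, are major events unlikely to be missed for want of two questionings. This stands.

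**Conclusion.** The protocol does not state a common AE-assessment schedule for the two arms, and its visit text can be read as 4 against 2 first-week contacts (ratio 1.0 to 3.0 across readings). The between-arm AE comparison is therefore at risk of differential ascertainment against injection, mainly for mild transient events. It would go too far to say that the comparison is biased, or that injected eyes will have twice the recorded AEs: the first requires settling a contradiction that the documents leave open, the second an unsupported recall assumption.

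The size is unknown. On the 4-to-2 count, the spurious ratio runs from near 1.0 with high ward and spontaneous capture to about 1.8 with none and 10% detection per contact. These figures rest on assumed detection rates, equal true risk and independent contacts. Events actually caused by the injection, such as the needle perforation named in section 6.3, are true harms and not part of this artefact.

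**What to change.** - **Protocol, visits.** Reconcile sections 3.1, 3.4, 3.5, 4.3, 4.4.3 and 6.2 on which visits controls have, including whether there is a sham procedure.
- **Protocol, AE questioning.** Amend 3.4.2, 3.4.5 and 3.6 so that both arms receive the same scripted AE questions and AE form at the procedure time point and on Day 5. Existing ward or study staff can do this, arranged so that the physician who performs the repeat scraping is not unmasked. State also whether AEs are asked about at Week 1, where 3.4.6 and the schedule differ.
- **SAP section 5.** Keep all AEs, however detected, in the main between-arm comparison and in the DSMC harm review. Add a supportive comparison limited to time points common to both arms, and flag events detected only at an injection procedure. The harm review should not be restricted to events elicited at common visits: that would take true injection harms out of the main comparison and drop observed and spontaneous reports.

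The cost is a short protocol clarification, a brief SAP addition and two short extra AE entries per control participant, all of whom are already inpatients on those days.
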